7.3. EXPAREL (bupivacaine liposome injectable suspension)

Bupivacaine is one of the longer-acting local anesthetics, but even so it has a limited duration of action after local administration, usually less than 8 hours. EXPAREL is a bupivacaine liposome injectable suspension. It consists of microscopic spherical, multivesicular liposomes (DepoFoam[®] drug delivery system), organized in a honeycomb-like structure comprising numerous non-concentric internal aqueous chambers containing a bupivacaine base at a concentration of 13.3 mg/mL. Each chamber is separated from adjacent chambers by lipid membranes. The lipids (phospholipids, cholesterol, and triglycerides) are naturally occurring or close analogs of endogenous lipids. Bupivacaine is slowly released from the DepoFoam particles by a complex mechanism involving reorganization of the barrier lipid membranes and subsequent diffusion of the drug over an extended period of time. EXPAREL has been noted in infiltration studies to have a bimodal curve (Apseloff 2013), with an initial peak occurring at approximately 0 to 2 hours and a second peak at approximately 24 to 48 hours (Hu 2013).

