6.7.2 Pharmacokinetic Parameters Calculation Methods

Nonsterospecific assay is used for the measurement of bupivacaine concentration. Pharmacokinetic parameters will be calculated by noncompartmental analysis (NCA) method from concentration-time data following these guidelines:

- Actual sampling times relative to study drug administration will be used for all calculations of the PK parameters. If there is any doubt as to the actual time a sample was taken, then the scheduled time will be used.
- Concentrations from unscheduled PK blood samples will be used in the analysis of the parameters.
- There will be no imputation of missing concentration data.
- For the summaries of concentrations and for calculation of area under the curve (AUC) from bupivacaine plasma concentrations, concentrations below the limit of quantification (BLOQ) will be handled as follows:
 - Pre-dose values will be set to zero.
 - BLOQ values between the dosing time and the first time point above lower limit of quantification (LLOQ) will be set to 0.
 - BLOQ values at time points between two measurable concentration values will be set to ½ of LLOQ (lower limit of quantification).
 - All remaining BLOQ values will be set to missing.

The following PK endpoints will be determined using non-compartmental methods:

- Area under the plasma concentration-versus-time curve (AUC0-∞ and AUC0-last). The AUC0-last from the time of dosing to the time of the last quantifiable concentration will be calculated using the linear trapezoidal method. The AUC0-∞ from the time of dosing (zero) to infinity will be calculated as sum of AUC0-last and residual area Ct/λz.
- Maximum plasma concentration (Cmax) and time of Cmax (Tmax).
- The apparent terminal elimination half-life (t1/2el). t1/2el will be calculated as $\log_e(2)/\lambda_z$. The apparent terminal elimination rate constant (λ_z) will be estimated at terminal phase by linear regression after log-transformation of the concentrations:
 - Only those data points that are judged to describe the terminal log-linear decline will be used in the regression.
 - A minimum number of three data points in the terminal phase will be used in calculating λ_z with the line of regression starting post the Cmax data point (Cmax will not be part of the regression slope) and including the last point above LLOQ value (Ct).
 - An appropriate number of decimal places will be used for λ_z to enable the reported value of terminal half-life (t1/2el) to be calculated.

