6.7.3 Pharmacokinetic Concentrations and Variables

A complete data listing will be provided for all PK bupivacaine concentration data. Concentrations that are BLOQ will be indicated in the listing.

A plot of bupivacaine concentration-time data, with original scale and semi-log scale overlain on the same page will be created for each individual subject.

If different than the preceding plot, a plot of dose-normalized concentration-time data, with the original scale and semi-log scale overlaid on same page, will also be created for each individual subject.

Plasma bupivacaine concentrations for each formulation will be summarized at each nominal time window (any out-of-window results would be shown only in a listing). The following descriptive statistics

will be presented: n, geometric mean, arithmetic mean, SD, %CV, median, minimum and maximum. Results will be summarized by treatment group (EXPAREL or bupivacaine HCl) for Group 1 and by surgery type (cardiac or spine) for Group 2. Plots of mean bupivacaine concentration over time will be created with the original scale and semi-log scale overlain on the same page. If the number of subjects in a group is less or equal to 3, then individual concentration over time curves will be plotted instead of the mean concentration. For group 1, there will be two plots overlain for the two treatments. For group 2, there will be two separate plots for the two types of surgery.

Pharmacokinetics parameters will be presented in the data listings and descriptive summary statistics, including the arithmetic mean, median, minimum, maximum, standard deviation, %CV of mean, geometric mean, %CV of geometric mean. Differences will be compared between the two formulations using single factor ANOVA.

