	Mean (%CV)	xx.x (xx.x)	xx.x (xx.x)
	SD	x.xx	X.XX
	Median	XX.X	XX.X
	Geometric Mean (%CV)	XX.X	XX.X
	Minimum, Maximum	XX, XX	XX, XX
	p-value *	0.xxx	
AUC(0-last) (hr*ng/mL)	n	XX	XX
	Mean (%CV)	xx.x (xx.x)	XX.X (XX.X)
	SD	x.xx	X.XX
	Median	XX.X	XX.X
	Geometric Mean (%CV)	XX.X	XX.X
	Minimum, Maximum	XX, XX	XX, XX
	p-value *	0.xxx	

* 2-sided t-test

Source: list SAS datasets used to create table SAS X.Y

ddmmmyyyyThh:mm program name

Note to programmer: Other Pharmacokinetic parameters to appear on this table are, in order of

appearance: Cmax (ng/mL), Tmax, t1/2el (hr), CL/F (L/hr), and Vd (L). Use this template also for tables:

Table 14.4-1.2: Summary of EXPAREL Pharmacokinetic Parameters (Group 2: 6 to < 12 years) - Spine Surgery - PK Population

Table 14.4-1.3: Summary of EXPAREL Pharmacokinetic Parameters (Group 2: 6 to < 12 years) - Cardiac Surgery - PK Population

Table 14.4-1.4: Summary of EXPAREL Pharmacokinetic Parameters (Both Groups: 6 to < 17 years) - Spine Surgery - PK Population

(Page X of Y)

Protocol: 402-C-319

Table 14.4-3.1: Summary of EXPAREL Pharmacokinetic Plasma Concentrations (ng/mL) (Group 1: 12 to <17 years) - PK Population

		EXPAREL	Bupivacaine HCl
	Statistic	[N=XX]	[N=xx]
15 Minutes	n	XX	XX
	Mean (%CV)	xx.x (xx.x)	xx.x (xx.x)
	SD	X.XX	X.XX
	Median	XX.X	XX.X
	Geometric Mean (%CV)	xx.x (xx.x)	xx.x (xx.x)
	Minimum, Maximum	XX, XX	XX, XX
30 Minutes	n	XX	xx
	Mean (%CV)	xx.x (xx.x)	xx.x (xx.x)
	SD	X.XX	X.XX
	Median	XX.X	XX.X
	Geometric Mean (%CV)	xx.x (xx.x)	xx.x (xx.x)
	Minimum, Maximum	XX, XX	XX, XX

Source: list SAS datasets used to create table

ddmmmyyyyThh:mm

SAS X.Y

program name

Note to programmer: Other Pharmacokinetic Plasma Concentration timepoints to appear on this table are, in order of appearance: 45 Minutes, 1 - 1.25 Hours, 2 - 3 Hours, 10 - 18 Hours, 24 - 36 Hours, and 42 - 60 Hours. Use this template also for tables:

Table 14.4-3.2: Summary of EXPAREL Pharmacokinetic Plasma Concentrations (ng/mL) (Group 2: 6 to < 12 years) - Spine Surgery - PK Population

Table 14.4-3.3: Summary of EXPAREL Pharmacokinetic Plasma Concentrations (ng/mL) (Group 2: 6 to < 12 years) - Cardiac Surgery - PK Population

Note to programmer: Change timepoints to: 15 Minutes, 30 Minutes, 45 Minutes, 1 - 1.25 Hours, 15 - 25 Hours, 30 - 40 Hours, 45 - 55 Hours, and 64 - 72 Hours.

Table 14.4-3.4: Summary of EXPAREL Pharmacokinetic Plasma Concentrations (ng/mL) (Both Groups: 6 to < 17 years) - Spine Surgery - PK Population

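### Linear trapezoids across an unsampled 7–16 h gap overstate the comparator's non-compartmental AUC when sample 6 is quantifiable, which tilts the Group 1 formulation comparison

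*SAP*

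**What the plan says.** SAP 6.7.2 sets the integration rule: "The AUC0-last from the time of dosing to the time of the last quantifiable concentration will be calculated using the linear trapezoidal method". It uses actual times: "Actual sampling times relative to study drug administration will be used for all calculations of the PK parameters". AUC0-inf builds on the same quantity; from time zero it "to infinity will be calculated as sum of AUC0-last and residual area" Ct/λz. CL/F and Vd/F both have AUC0-inf in the denominator. For values below quantification after the last measurable sample, the rule is: "All remaining BLOQ values will be set to missing".

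Group 1 has spine surgery only, so both randomised arms follow the spine schedule. After the 15- and 30-minute samples, the programmer note under SAP Table 14.4-3.1 lists "45 Minutes, 1 - 1.25 Hours, 2 - 3 Hours, 10 - 18 Hours, 24 - 36 Hours, and 42 - 60 Hours".

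SAP 6.7.3 adds the comparison: "Differences will be compared between the two formulations using single factor ANOVA". The shell for Table 14.4-1.1 prints a p-value under each AUC, footnoted as a two-sided t-test, and puts CL/F and Vd on the same template.

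**The concern.** On an exponential decline, the chord between two samples lies above the curve. The wider the gap in half-lives, the larger the excess. The comparator is immediate-release bupivacaine, of which Protocol 7.3 says "it has a limited duration of action after local administration, usually less than 8 hours". That is a statement about effect, not a half-life, but a steep fall between 3 h and 10 h is the natural expectation. EXPAREL is described there as bimodal, "with an initial peak occurring at approximately 0 to 2 hours and a second peak at approximately 24 to 48 hours", so its curve over the same gap is not a simple decline. One rule on one schedule therefore gives a different error in each arm.

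At stake is the SAP's own exposure comparison. If the comparator's AUC is overstated, EXPAREL's relative exposure looks lower than it is, which is the less cautious direction in a paediatric PK and safety study. The size also shifts with where in the 10–18 h window sample 6 happened to be drawn.

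**Working it through.** The plan states no AUC, half-life or bias, so there is no figure to reproduce.

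**Inputs from the documents.** Linear rule at actual times; spine windows. Shortest gap between samples 5 and 6: 10 − 3 = 7 h. Longest: 18 − 2 = 16 h.

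**Inputs assumed.** Half-life 2.7, 3.5, 5, 6, 8 or 10 h; absorption half-life 0.2 or 0.5 h; EXPAREL early-release fraction 3% or 10%, with the remainder released on a gamma curve peaking at 24, 36 or 48 h; concentration zero at time 0; every sample quantifiable.

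**Step 1: the gap alone.** If concentration falls exponentially by a factor r, linear area ÷ true area = (1 + 1/r)·ln r ÷ [2(1 − 1/r)]. This needs no half-life.

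- r = 2: 1.5 × 0.693 ÷ 1.0 = 1.04
- r = 4: 1.25 × 1.386 ÷ 1.5 = 1.16
- r = 10: 1.1 × 2.303 ÷ 1.8 = 1.41
- r = 20: 1.05 × 2.996 ÷ 1.9 = 1.66

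At window midpoints the gap is 14 − 2.5 = 11.5 h, so r = 2^(11.5 ÷ half-life). A 10 h half-life gives r = 2.2 and +5% over the gap. A 3.5 h half-life gives r = 9.8 and +40%.

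**Step 2: the whole comparator curve.** Model: one compartment with first-order absorption. Error = trapezoidal AUC0-last ÷ exact integral to the same time − 1, averaged over 2,000 schedules drawn uniformly within the spine windows. Ranges run over the two absorption half-lives.

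| Assumed half-life (h) | Linear, group mean | Linear-up/log-down |
|---|---|---|
| 2.7 | about +39% | down to −3.2% |
| 3.5 | +28.4% to +29.8% | −2.8% to −0.6% |
| 5 | +18.0% to +19.5% | −2.2% to −0.4% |
| 6 | +14.1% to +15.6% | −1.9% to −0.4% |
| 8 | +9.4% to +10.7% | −1.5% to −0.3% |
| 10 | +6.7% to +7.8% | −1.3% to −0.2% |

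Single schedules run from +3% to +70%.

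**Step 3: EXPAREL on the same schedules.** With 3–10% early release, the linear group-mean error is −6.0% to +7.4%, and single schedules run from −19% to +24%. Larger early-release fractions raise the top of the group-mean range to roughly +14%. A smaller simulation (60 schedules per scenario, early release 3–20%) reached +18%. Linear-up/log-down gives −7.2% to +2.4% for 3–10% early release.

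**Step 4: the EXPAREL/HCl AUC ratio.** Example: half-life 3.5 h, absorption half-life 0.5 h, 10% early release, peak at 36 h. The ratio is multiplied by 1.003 ÷ 1.284 = 0.78, so it is understated by 22%. Over all sets with 3–10% early release, the linear rule understates the ratio by about 5–31%. Under linear-up/log-down the ratio is off by about −7% to +5%.

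**Step 5: what inherits the error.** For the comparator, the AUC0-inf error is within about one percentage point of the AUC0-last error. With inflation of 5–40%, CL/F = Dose ÷ AUC0-inf is multiplied by 1/1.05 = 0.95 down to 1/1.40 = 0.71, so it is about 5–29% too low. Vd/F carries the same factor, because λz comes from regression and not from the trapezoids. Cmax does not use the rule.

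**Step 6: the condition.** If comparator samples 6–8 are all below quantification, they become missing and AUC0-last ends at 2–3 h. The trapezoid error to that point is about −1%, but the area is 50–86% below true AUC0-inf. At a 2.7 h half-life, sample 6 is only about 1–10% of Cmax, so the top of the inflation range depends on an LLOQ that is not stated.

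**The case against.** The strongest reply has four parts.

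- **The sizes are assumed.** Half-life, absorption, release shape and LLOQ are all missing from the documents. This stands. A reader might take some single inflation figure as a property of the plan, or infer that EXPAREL is almost free of error. Neither is supported: the comparator's error varies several-fold with half-life, and the protocol's bimodal description does not establish a flat or rising EXPAREL curve across the gap. The arms must also be compared on the same footing, both as group means over random in-window times.
- **The direction is conditional.** This also stands. Comparator AUC is overstated only when the gap is crossed. If samples 6–8 are all below quantification, AUC0-last falls short instead.
- **The scope is narrow.** A reader might infer that the study's PK endpoints are biased. They are not: Protocol 12.2 takes them from a population model that uses no trapezoid, SAP 6.11 presents the non-compartmental analysis as an addition, and Protocol 15.1 plans no formal hypothesis test. The SAP comparison has no margin or decision rule. The arms receive 4 and 2 mg/kg, so raw AUCs are not dose-matched in any case. Still, CL/F is dose-normalised and carries the bias. Population-PK results are reported separately, so the SAP's own parameter tables are the non-compartmental ones.
- **The alternative rule is imperfect.** True, but for the comparator on the spine schedule it is far closer.

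None of this removes the direction when sample 6 is measurable. In every assumption set run over random schedules, the comparator was inflated and the ratio was pulled down.

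**Conclusion.** The point holds conditionally. Given a quantifiable sample 6, the SAP's rule overstates bupivacaine HCl AUC by roughly 5–40% as a group mean, for assumed half-lives of 10 down to 2.7 h. EXPAREL's group-mean error is roughly −6% to +14%, depending on its early-release fraction. Individual schedules go wider in both arms. The non-compartmental comparison of AUC, CL/F and Vd/F is therefore biased by formulation, with EXPAREL's relative exposure tending to look too low.

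The direction follows from the schedule and the rule. The size rests on the assumed one-compartment comparator and EXPAREL release shapes. The change is worth making, but the study's primary PK characterisation does not depend on it.

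**What to change.** In SAP 6.7.2, replace the linear trapezoidal method with the linear-up/log-down trapezoidal method: linear when concentrations rise or are equal, logarithmic when they fall and both are above zero. Apply it to AUC0-last and AUC0-inf in all groups, and keep the linear result as a sensitivity listing.

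The cost is one sentence and a change of integration setting. AUCs become slightly less comparable with any earlier study that used the linear rule.

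The error is reduced, not removed. The cardiac schedule has a longer gap, from 1–1.25 h to 15–25 h (13.75 to 24 h). In simulation, the group-mean error there fell from as much as +43% with the linear rule to about +20%. Under some release shapes, EXPAREL's own error becomes a few points more negative (−7.2% against −6.0% at the lower end). The new rule does not cure truncation when late comparator samples are below quantification, so the report should state how many subjects had AUC0-last ending at 2–3 h.

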- Apparent clearance (CL/F) will be estimated as Dose/AUC0-∞.
- Apparent volume of distribution (Vd/F) will be estimated based on the teriminal phase as Dose/($\lambda_z \cdot AUC0-\infty$).

In addition, a population PK modeling will be performed using all PK data collected during the study. The population PK analysis plan will be developed separately.

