Table 14.3-5.1.2: Summary of Incidence of Serious Treatment-Emergent Adverse Events (TEAEs) (Group 2: 6 to < 12 years) - Safety Population

Table 14.3-5.1.3: Summary of Incidence of Serious Treatment-Emergent Adverse Events (TEAEs) (Both Groups: 6 to < 17 years) - Spine Surgery - Safety Population

Note to programmer: Use mock-up 14.3-4.2.1 for the following:

Table 14.3-6.1.1: Summary of Incidence of Treatment-Emergent Adverse Events (TEAEs) of Special Interest (Group 1: 12 to <17 years) - Safety Population

Table 14.3-6.1.2: Summary of Incidence of Treatment-Emergent Adverse Events (TEAEs) of Special Interest (Group 2: 6 to < 12 years) - Safety Population

Table 14.3-6.1.3: Summary of Incidence of Treatment-Emergent Adverse Events (TEAEs) of Special Interest (Both Groups: 6 to < 17 years) - Spine Surgery - Safety Population

Note to programmer: Use mock-up 14.1-5.1.1 for the following:

Table 14.3-7.1.1: Tabulation of Incidence of Prior Medications (Group 1: 12 to <17 years) - Safety Population

Table 14.3-7.1.2: Tabulation of Incidence of Prior Medications (Group 2: 6 to < 12 years) - Safety Population

Note to programmer: On these tables change the footnote 'Intraoperative medications are those indicated as such by the investigator' to read 'Prior medications are those stopped before start of study drug administration.'

Table 14.3-7.1.3: Tabulation of Incidence of Prior Medications (Both Groups: 6 to < 17 years) - Spine Surgery - Safety Population

Table 14.3-8.1.1: Tabulation of Incidence of Concomitant Medications (Group 1: 12 to <17 years) - Safety Population.

Table 14.3-8.1.2: Tabulation of Incidence of Concomitant Medications (Group 2: 6 to < 12 years) - Safety Population.

Note to programmer: On these tables change the footnote 'Intraoperative medications are those indicated as such by the investigator' to read 'Concomitant medications are those taken between the start of study drug administration and discharge from study and are not designated intraoperative medications.' Note that a concomitant medication can start prior to start of study drug and be ongoing.

Table 14.3-8.1.3: Tabulation of Incidence of Concomitant Medications (Both Groups: 6 to < 17 years) - Spine Surgery - Safety Population.

(Page X of Y)

Protocol: 402-C-319

Table 14.4-1.1: Summary of EXPAREL Pharmacokinetic Parameters (Group 1: 12 to <17 years) - PK Population

		EXPAREL	Bupivacaine HCl
	Statistic	[N=xx]	[N=xx]
AUC(0-inf) (hr*ng/mL)	n	XX	XX

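### SAP 6.7.2 neither limits nor reports the extrapolated share of AUC0-∞, and on the spine schedule the terminal slope has to be fitted across EXPAREL's second peak

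*SAP*

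**What the plan says.** SAP 6.7.2 calculates AUC0-last by a stated rule ("will be calculated using the linear trapezoidal method"). AUC0-∞ then "will be calculated as sum of AUC0-last and residual area" Ct/λz, and no condition is attached. The result is carried forward: "Apparent clearance (CL/F) will be estimated as" Dose/AUC0-∞, and Vd/F is Dose/(λz·AUC0-∞).

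Three rules govern λz:
- "A minimum number of three data points in the terminal phase will be used in calculating" it;
- the regression starts after Cmax ("Cmax will not be part of the regression slope") and includes the last point above LLOQ;
- "Only those data points that are judged to describe the terminal log-linear decline will be used in the regression".

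There is no fit criterion, no largest acceptable extrapolated share, and no rule for flagging AUC0-∞, CL/F, Vd/F or t1/2el. The mock-up for "Table 14.4-1.1: Summary of EXPAREL Pharmacokinetic Parameters (Group 1: 12 to <17 years) - PK Population" and Listing 16.2-9.5.1.1 show AUC(0-inf) beside AUC(0-last) but no percent extrapolated. SAP 6.7.3 compares the two formulations on these parameters by single-factor ANOVA.

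Protocol 7.3 describes EXPAREL as bimodal, "with an initial peak occurring at approximately 0 to 2 hours and a second peak at approximately 24 to 48 hours". The spine schedule (Protocol Table 2, SAP Table 2) ends with samples at 10–18, 24–36 and 42–60 h.

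**The concern.** The residual Ct/λz is sound only if the fitted points describe elimination after release is essentially over. On the spine schedule at most two scheduled samples can follow a peak at 24–48 h, yet three are required. A slope fitted through points that straddle the second peak partly measures continuing release. It is too shallow, and the division by λz magnifies the error.

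At stake are the EXPAREL values of AUC0-∞, CL/F, Vd/F and t1/2el in the SAP's noncompartmental tables, and their comparison with bupivacaine HCl in Group 1, where every child has spine surgery and each Part 1 arm has 15. With arms that small, a few extreme extrapolations can dominate an arithmetic mean and SD. Nothing in the planned output would tell the reader how much of each AUC0-∞ was observed.

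**Working it through.** The plan states no extrapolated share, so there is no figure to reproduce.

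**1. Which children get a λz (spine, scheduled samples, last sample quantifiable).** Count the samples after Cmax:
- Cmax at sample 6, 7 or 8: 2, 1 or 0 remain. Fewer than three, so λz, AUC0-∞ and CL/F cannot be calculated.
- Cmax at sample 5 (2–3 h): exactly samples 6, 7 and 8 remain.
- Cmax earlier: more points are available, but a run of at least three ending at the last one still contains samples 6–8.

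So every estimable slope contains the points at 10–18, 24–36 and 42–60 h.

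**2. What such a slope does.** Take mid-window times 14, 30 and 51 h, with assumed relative concentrations and an assumed early peak of 100 at 0.75 h.
- λz = −Σ(t − t̄)ln C / Σ(t − t̄)², with t̄ = 31.67 and Σ(t − t̄)² = 688.67.
- For 60/50/40, Σ(t − t̄)ln C = −7.535, so λz = 7.535/688.67 = 0.0109 per h and the half-life is 0.693/0.0109 ≈ 63 h.
- Residual = 40/0.01094 ≈ 3,656.
- AUC0-last = 2,843. Of this, 16×(60+50)/2 + 21×(50+40)/2 = 880 + 945 = 1,825 lies after 14 h, and the remaining 1,018 is the assumed early part.
- Extrapolated share = 3,656/(2,843 + 3,656) = 56%.

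The same steps for other assumed triplets:

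| C at 14/30/51 h | λz (per h) | Half-life (h) | Share extrapolated |
|---|---|---|---|
| 60/50/40 | 0.0109 | 63 | 56% |
| 50/60/40 | 0.0067 | 103 | 67% |
| 55/65/50 | 0.0031 | 225 | 84% |
| 60/40/15 | 0.0379 | 18 | 14% |

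The second and third rows do not decline throughout. The first does, and still has more than half its AUC0-∞ extrapolated.

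**3. Size against a known truth.** The SAP rules were applied to simulated curves: a fast fraction plus delayed release, one-compartment elimination, 10% noise, samples drawn in the spine windows. All curve parameters are assumptions.
- AUC0-∞/true: median 1.17–1.27, 95th percentile 1.7–5.5, when any three points with a negative fitted slope are accepted.
- If the three points must also decline: median 1.16–1.19, 95th percentile 1.6–1.9.
- A separate run (fast fraction 20–30%, mean release 24–36 h, half-life 3–5 h; 3,493 estimable of 5,400 profiles, no decline requirement) gave a median of 1.30 and a 95th percentile of 7.3. The median extrapolated share was 26%, against a mean true tail of 9%.
- A wider grid (fast fraction 0.1–0.4, release mode 20–40 h, half-life 3 or 6 h) gave medians of 1.03 to 5.81 over all calculable spine settings. The lowest 5th percentile was 0.83, so understatement is possible but less usual.

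CL/F moves inversely: an AUC0-∞ 15–25% too high gives CL/F at 1/1.15 = 0.87 to 1/1.25 = 0.80 of true.

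**4. Effect of a limit.** With an assumed 20% limit, about 30–60% of estimable children are flagged (67% in one other set of assumed curves). Those kept still show a median excess of 11–15%, and they have shorter true tails: in one setting a mean of 7%, against 14% in all estimable children.

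**The case against.** Several points on the other side stand.

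- **Status.** A reader might infer that the trial's primary PK results are biased. The documents do not support that. Protocol 12.2 makes the PK endpoints model-predicted, and SAP 6.11 describes the noncompartmental work as an addition. The population model does not use Ct/λz.
- **Judgement can reject.** The wording on judged points lets the analyst declare λz not estimable, and Listing 16.2-9.5.1.1 already defines ND. Extreme ratios come largely from triplets that do not decline, which a careful analyst would refuse. This removes most of the upper tail but leaves the median near 1.2.
- **Missing rather than wrong.** Where the second peak clearly exceeds the first, AUC0-∞ was calculable in only 0–4% of simulated spine profiles. How many children would be affected is unknown.
- **Not all extrapolation.** The linear trapezoid over wide gaps can itself add up to 9% in some distinct-peak spine settings.
- **One arm only?** It is tempting to say the error falls on EXPAREL alone, because a 3–5 h half-life leaves at most 2^(−42/5) = 0.3% of the AUC beyond 42 h. That presumes quantifiable drug at 42 h. No LLOQ is given, and trailing BLOQ values are set to missing. With a last quantifiable sample at 10 h, mono-exponential decay leaves 2^(−10/3) = 10% to 2^(−10/5) = 25%.
- **Already derivable.** The share follows from the two listed AUCs, and the tables include the median and geometric mean. But no planned output summarises the share or acts on it.

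**Conclusion.** The point holds for the SAP's added noncompartmental analysis on the spine schedule. Following the stated rules tends to overstate EXPAREL AUC0-∞ and understate CL/F, and the planned output neither limits nor shows the extrapolation. The mechanism follows from the documents alone: the three-point rule, the sample times and the stated second peak. It assumes only scheduled samples and a quantifiable last one; an unscheduled sample, which SAP 6.7.2 would use, could change the count.

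The size does not follow from the documents. In the main assumed settings the median overstatement is roughly 15–25%. The 95th percentile is about 1.6–1.9 times true if clearly non-declining points are rejected, and up to about 5 times if they are not; other assumed curves go beyond these ranges in both directions. Severalfold inflation should therefore not be read as the expected result of the plan. This should be changed before analysis, but it does not threaten the protocol's model-predicted endpoints.

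**What to change.** In SAP 6.7.2 and Tables 14.4-1.x:

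1. List the percent of AUC0-∞ extrapolated for each child, and summarise it by arm.
2. State that λz, and everything derived from it, is ND when the three terminal points do not decline.
3. Make AUC0-last the main noncompartmental exposure measure for the formulation comparison, alongside the model-predicted AUC.
4. Flag AUC0-∞, CL/F, Vd/F and t1/2el when the extrapolated share exceeds a pre-set limit (20%, for example, is an assumed convention and not in the documents). Summarise them with and without flagged children, giving the numbers flagged and not determined in each arm.

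The cost is SAP wording, one table row and one listing column; sampling does not change. The downside is that fewer EXPAREL children contribute an unflagged AUC0-∞. Because those retained have shorter tails and some excess remains, the restricted summary is supportive only. For that reason, dropping flagged children outright is not recommended.
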